3.3 General study level definitions

3.3.1 Analysis time points

3.3.1.1 First dose of study drug

Unless otherwise noted, all references to the first dose of study drug in this SAP refer to the first dose of study drug during EP0132.

3.3.1.2 Relative day

Relative day will be calculated as the current date minus the date of first dose of study drug for days prior to the first dose of study drug, and the current date minus the date of first dose of study drug plus 1 for days on or after the date of first dose of study drug and prior to or on the day of last study drug dose (eg, the day of first dose will be Day 1 and the day prior to first dose will be Day -1). For days after the last dose of study drug, relative day will be calculated as the current date minus the date of last dose of study drug and will include a '+' to denote post-treatment days (eg, the day after the last dose will be Day +1). Relative day will not be calculated for partial dates.

3.3.1.3 Early Discontinuation Visit

The EDV will be attended if the participant discontinues study treatment early for any reason and is not considered a completer as defined in [Section 3.3.5](#).

3.3.1.4 Final Visit

The FV refers to the last visit for study participants for completers as defined in [Section 3.3.5](#). All FVs will be mapped to a scheduled visit where applicable, as per [Section 3.3.8](#), and summarized accordingly.

3.3.2 Study periods

For reporting purposes, the Evaluation Period will last from the date of first dose in EP0132 until the FV inclusive, or from the date of first dose in EP0132 until the EDV inclusive for study participants who prematurely discontinue the study. The Evaluation Period may be truncated at the Month 24 YEV for the reporting of the absence seizure freedom based on seizure data (diary and EEG). It is expected that the first dose in EP0132 will be taken in the evening of the EV. For

participants who complete the study at the FV, the Overall Period will include the Evaluation Period only. Otherwise, for participants who are not required to down-titrate as a dose of 1mg/kg/day (50mg/day for study participants with body weight $>50\text{kg}$) is reached at the FV or EDV, the Overall Period will include the Evaluation Period and Safety Period. Otherwise, the Overall Period will include the Evaluation Period, Down-Titration Period and Safety Period.

For study participants who discontinue BRV treatment following the EDV or FV and a dose of $>1\text{mg/kg/day}$ ($>50\text{mg/day}$ for study participants with body weight $\geq 50\text{kg}$) is reached at the EDV or FV respectively, the BRV dose will be reduced by a maximum of half the dose every week for a maximum of 4 weeks until a dose of 1mg/kg/day (50mg/day for study participants with body weight $>50\text{kg}$) is reached (Down-Titration Period). A DTV will be performed at the end of the Down-Titration Period, and study drug will be discontinued at the DTV. Otherwise, for study participants who will discontinue BRV treatment following the EDV or FV and a dose of 1mg/kg/day (50mg/day for study participants with body weight $>50\text{kg}$) is reached at the EDV or FV respectively, down titration will not be applicable.

After 2 weeks free of study drug (Safety Period), study participants will complete the SV.

The definitions of the Evaluation, Down-Titration, Safety Follow-up, and Overall Periods are provided in [Table 3-2](#). Adverse events are assigned to a study period based on the date of onset. All other measurements are assigned based on the date of assessment.

Table 3-2: Definition of study periods

Period	Definition	Algorithmic rule
Evaluation Period	From the date of first dose in EP0132 inclusive until: 
• FV inclusive for participants who complete the study, or• EDV inclusive for participants who discontinue the study early	Day of first dose in EP0132 eCRF date inclusive to 
• If the participant completed the study: day of FV eCRF date inclusive;• Else if the participant attended the EDV: day of EDV eCRF date inclusive;• Else if the participant did not attend one of these visits (eg, is lost to follow up): day of last study medication as recorded on the Study Termination eCRF inclusive;• Else if the participant died: the date of death inclusive.
Down-Titration Period	
• From the day after the FV inclusive for study participants who complete the study and	
• If the participant completed the study and subsequently down-titrated: day after the FV eCRF date inclusive;

Table 3-2: Definition of study periods

Period	Definition	Algorithmic rule
	
subsequently discontinue BRV, or
 
From the day after the EDV inclusive for study participants who discontinue the study early and subsequently discontinue BRV 
to
 
the DTV inclusive.
	
If the participant attended the EDV: day after the EDV eCRF date inclusiveIf the participant attended the DTV: day of DTV eCRF date inclusive;Else if the participant did not attend the DTV: day of last study medication as recorded on the Study Termination eCRF inclusive;Else if the participant died: the date of death inclusive.
Safety Period	
In study participants who entered the Down-Titration Period: From the day after the DTV until the day of the SV inclusive.
 
In study participants who did not enter the Down-Titration Period as a dose of 1mg/kg/day (50mg/day for study participants with body weight >50kg) is reached at FV: from the day after
	
In study participants who entered the Down-Titration Period (attended the FV or the EDV and is down-titrating as indicated on the Study Drug Dispensation and Administration eCRF):
 
From the day after the DTV eCRF date inclusive
 
to
 
If the study participant attended the SV: day of the SV eCRF date inclusive;Else if the study participant was lost to follow-up: day of the last contact date on the Study Termination eCRF inclusive;Else if the study participant died: the date of death inclusive. 
In study participants who did not enter the Down-Titration Period as a dose of 1mg/kg/day (50mg/day for study participants with body weight >50kg) is reached at FV:
 
From the day after the FV eCRF date inclusive

Table 3-2: Definition of study periods

Period	Definition	Algorithmic rule
	the FV until the day of the SV inclusive.	to 
• If the study participant attended the SV: day of the SV eCRF date inclusive;• Else if the study participant was lost to follow-up: day of the last contact date on the Study Termination eCRF inclusive;• Else if the study participant died: the date of death inclusive.
Overall Period	In study participants who did not enter the Down-Titration Period as a dose of 1mg/kg/day (50mg/day for study participants with body weight >50kg) is reached at EDV: from the day after the EDV until the day of the SV inclusive.	In study participants who did not enter the Down-Titration Period as a dose of 1mg/kg/day (50mg/day for study participants with body weight >50kg) is reached at EDV: From the day after the EDV eCRF date inclusive to 
• If the study participant attended the SV: day of the SV eCRF date inclusive;• Else if the study participant was lost to follow-up: day of the last contact date on the Study Termination eCRF inclusive;• Else if the study participant died: the date of death inclusive.

Table 3-2: Definition of study periods

Period	Definition	Algorithmic rule
	
 • FV inclusive for participants who transition to another BRV study or a managed access program or who convert to commercial BRV. The latest of the DTV, FV or EDV inclusive for participants who discontinue the study and do not enter the Safety Period 	
 • Else if the study participant did not attend the SV: maximum day of the DTV, FV or EDV eCRF date inclusive (note that for participants who transition to another BRV study or a managed access program, this is expected to be the FV); • Else if the study participant was lost to follow-up: day of the last contact date on the Study Termination eCRF inclusive; • Else if the study participant died: the date of death inclusive.

BRV=brivaracetam, eCRF=electronic case report form, DTV=Down-Titration Visit, EDV=Early Discontinuation Visit, FV=Final Visit, SV=Safety Visit

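### SAP Table 3-2 tests for a missed Safety Visit before loss to follow-up and death, so the Overall Period can end before the TEAE window of last dose + 14 days

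*SAP*

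**What the plan says.** SAP 3.3.2 places events in periods by onset: "Adverse events are assigned to a study period based on the date of onset". Its text then builds the Overall Period from its parts. There are two exceptions. For "participants who complete the study at the FV, the Overall Period will include the Evaluation Period only". For those who do not need to taper, it is the Evaluation plus Safety Periods. For the rest: "Otherwise, the Overall Period will include the Evaluation Period, Down-Titration Period and Safety Period".

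The Overall Period row of Table 3-2 is less consistent.

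- **Algorithm column:** "Else if the study participant did not attend the SV: maximum day of the DTV, FV or EDV eCRF date inclusive". The loss-to-follow-up branch (end at last contact) and the death branch (end at death) come after it.
- **Definition column:** the visit-date end has a condition that the algorithm omits: "The latest of the DTV, FV or EDV inclusive for participants who discontinue the study and do not enter the Safety Period".

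Two other rows of the table matter here.

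- **Safety Period:** it starts the day after the DTV, or the day after the FV or EDV if there is no taper. If the SV is missed it ends at death or, for those lost, as follows: "Else if the study participant was lost to follow-up: day of the last contact date on the Study Termination eCRF inclusive".
- **Down-Titration Period:** "Else if the participant did not attend the DTV: day of last study medication as recorded on the Study Termination eCRF inclusive".

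The primary estimand (SAP Table 2-1) and SAP 10.2 both stop TEAE observation 14 days after the last dose. SAP 10.2 and 10.2.1 tabulate TEAEs for the Overall Period, the Evaluation Period and the three-month periods within the Evaluation Period.

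**The concern.** Loss and death before the SV are special cases of not attending it. Placed after the missed-SV branch, they can apply at most when no DTV, FV or EDV date exists. The general branch captures everyone else and ends the period at the last visit.

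TEAEs are the primary endpoint, and the Overall Period is the only AE tabulation period that extends beyond the FV or EDV. Events that can still be reported after a missed SV are likely to be serious or fatal, because Protocol 8.2.1 asks for SAEs up to 30 days after each participant's end of study. A few such events could fall outside the Overall Period incidence tables. The overview table in SAP 10.2.1 also has a death row based on the screened set, and the SAP does not say whether that row is limited to a period. It could therefore show one death beside zero TEAEs leading to death.

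**Working it through.** The plan gives no figure to reproduce. The check applies the rule as written to dated examples. All days are illustrative, and no dropout or event rate is assumed.

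**Which branches can be reached.** The opening branch of the Overall Period rule cannot be read in the available text. I take it to be SV attended, since the next one begins with an else and covers SV not attended. There are 2^6 = 64 combinations of SV, DTV, FV and EDV attended or not, lost or not, died or not. In 32 the SV was attended and in 32 it was not, so the first two branches use up all 64. If a programmer skips the missed-SV branch when there is no visit date to take, the later branches can apply there only.

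**Examples.** Overall end = latest of DTV, FV, EDV. Window end = last dose + 14. For a taper with the DTV missed I use the last dose taken during the taper (SAP 4.1.4.5), because the DTV-based definition in SAP 3.13.14 then gives no date.

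| Participant, SV missed | Overall end, Table 3-2 | End of component period | 10.2 window end |
|---|---|---|---|
| 1. No taper; EDV and last dose day 400, SAE onset day 405, death day 408 | 400 | Safety: 408 | 400 + 14 = 414 |
| 2. Taper, DTV missed; EDV day 400, fatal event and last dose day 420 | 400 | Down-Titration: 420 | 420 + 14 = 434 |
| 3. Taper; DTV and last dose day 414, death day 422 | 414 | Safety: 422 | 414 + 14 = 428 |
| 4. Taper; DTV and last dose day 414, lost, last contact day 424 | 414 | Safety: 424 | 414 + 14 = 428 |

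- **Case 1:** 405 > 400, so the SAE is out under Table 3-2. It is in under the 3.3.2 text (405 ≤ 408) and under 10.2 (405 ≤ 414).
- **Case 2:** the fatal event falls 420 − 400 = 20 days after the cut, although the participant was still on drug.
- **Cases 3 and 4:** 422 − 414 = 8 and 424 − 414 = 10 days are lost, all inside the window.

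**The definition column.** In Cases 1, 3 and 4 the participant has entered the Safety Period, so that column does not allow the visit-date end. In Case 2 no DTV took place, so the Safety Period never starts and the column does not contradict the cut. The conflict there is that the Down-Titration Period ends on day 420, outside the Overall Period that should contain it.

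**Maximum loss.** If the last dose is on the visit day (no taper, or DTV attended), it is 0 + 14 = 14 days. The taper lasts at most four weeks: "the BRV dose will be reduced by a maximum of half the dose every week for a maximum of 4 weeks". If the DTV is missed after a full taper, the loss is 28 + 14 = 42 days (days 401 to 442 for an EDV on day 400).

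**Participants who miss the SV but are neither lost nor dead.** The Safety Period row gives them no end date. The cut at the last visit still conflicts with the 10.2 window.

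**Scale of one event.** 1/140 = 0.71% of planned enrolment.

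**The case against.** The strongest reply is that SAP 10.2 states its own inclusion rule for AE summaries, running to last dose + 14 days. A programmer who follows it loses nothing in any of the cases. The text of 3.3.2 and the definition column also show the intent, and only one algorithm cell drops the qualifier. This stands as far as it goes: the loss depends on which text is programmed. But 10.2 also produces its tables by period, 3.3.2 assigns events to periods by onset date, and Amendment 1 added the Overall Period definition precisely because planned tables used it. Two programmers could reach different fatal TEAE counts in good faith.

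A reader might infer that deaths would vanish from the report. The documents do not support that. SAP 10.2.2 lists all AEs, serious AEs and deaths. Some events would also appear in the screened-set death row (10.2.1), or in the table of discontinuations due to AEs (5.1.3), which has no stated period limit. The last of these catches an event recorded as the reason for stopping, but not necessarily a later one.

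A reader might also infer that confining the Overall Period to the Evaluation Period for completers at the FV is a slip. The version history shows that it was added on purpose. The remaining difficulty is narrow: participants whom the investigator judges complete (SAP 3.3.5) and who stop brivaracetam at the FV still fall under the 10.2 window.

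Finally, for AE tables alone one sentence adopting last dose + 14 days would be enough. That is right. Reordering the branches is needed only so that the period definition agrees with its own parts.

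**Conclusion.** The point holds as an internal contradiction in a rule that feeds the primary endpoint tables. The visible branch order in Table 3-2 conflicts with the 3.3.2 text, the Safety Period row and the 14-day window. It conflicts with the definition column only for participants who entered the Safety Period. Participants who continue brivaracetam after the FV are not affected.

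If Table 3-2 governs, the exposure is up to 14 days of the window, or 42 days in the corner case of a missed DTV after a full taper. The number of participants affected cannot be derived from the documents. It is likely very small, and the overall TEAE percentage should barely move. The practical risk is to rare events: a single case can turn the fatal TEAE table from 1 to 0.

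The conclusion rests on the visible branches being in their true order and on the unreadable opening branch being SV attended. It is worth correcting because it is cheap and concerns serious and fatal events, not because a material bias is expected.

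A separate, minor point: Protocol 9.2 and 9.4.1 plan AE outputs for the Down-Titration and Safety Periods. SAP 3.2, 10.2 and 10.2.1 drop them, and SAP 3.12 does not declare the change. Overall minus Evaluation counts recover part of that detail.

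**What to change.** 1. In the Overall Period row of Table 3-2, test death, then loss to follow-up, before the missed-SV branch. Death should come first because the SAP version history takes last contact to be while the participant was alive. If the Case 1 participant were first recorded as lost with last contact on day 400, testing loss first would still end the period on day 400.
2. State that, for AE summaries of participants who stop brivaracetam, the Overall Period includes all TEAEs with onset up to last dose + 14 days as in SAP 10.2, whatever the SV attendance and with no cut at last contact. In Case 1 this gives day 414, and the SAE is counted.
3. State that the same window applies to investigator-determined completers who stop brivaracetam at the FV. Keep the FV as the end for participants who continue the drug.
4. As a separate item, restore the Down-Titration and Safety Period AE outputs, or declare and justify their removal in SAP 3.12.

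The cost is a reordered list and two sentences for items 1 to 3, and extra columns or one entry in 3.12 for item 4. No new data are needed. The death branch could also be moved up in the Evaluation and Down-Titration rows, but that is only tidying.

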3.3.3 Three- and six-month periods

A month is defined as 30 days and time intervals based on monthly durations are defined as a multiple of 30 days. The definitions of 3- and 6-month periods are described in [Table 3-3](#) and [Table 3-4](#) respectively.

Table 3-3: Definition of each 3-month period

Period	Days relative to date of first dose in EP0132
Months 1 to 3	1 to 90
Months 4 to 6	91 to 180
Months 7 to 9	181 to 270
Months 10 to 12	271 to 360
Months 13 to 15	361 to 450
Months 16 to 18	451 to 540
Months 19 to 21	541 to 630
Months 22 to 24	631 to 720
Months 25 to 27*	721 to 810
Months 28 to 30*	811 to 900
Months 31 to 33*	901 to 990
Months 34 to 36*	991 to 1080

Table 3-3: Definition of each 3-month period

Period	Days relative to date of first dose in EP0132
...	...

* These 3-month periods are only applicable for a subset of participants who remain in the EP0132 study past Month 24.

Table 3-4: Definition of each 6-month period

Period	Days relative to date of first dose in EP0132
Months 1 to 6	1 to 180
Months 7 to 12	181 to 360
Months 13 to 18	361 to 540
Months 19 to 24	541 to 720
Months 25 to 30*	721 to 900
Months 31 to 36*	901 to 1080
...	...

* These 6-month periods are only applicable for a subset of participants that remain in the EP0132 study past Month 24.

Three-month periods will be utilized for summaries and analyses of efficacy based on seizure data (diary data), AEs, and other safety endpoints. Six-month periods will be utilized for efficacy analyses of seizure data based on EEG, and consecutive and cumulative consecutive absence seizure freedom based on seizure data (EEG and diary data). For the analysis of AEs, participants will be included in 3-month period summaries if the end date of their Evaluation Period is on or after the first day of the 3-month period respectively.

Assessment visits are scheduled based on months calculated as 365.25/12 and thus are not fully aligned to the 3-month or 6-month periods described above. For example, the 7 to 12 month period would end at 360 days whereas the Month 12 visit is scheduled at 365 days. Similarly, the 19 to 24 month period would end at 720 days whereas the Month 24 visit is scheduled at 731 days. Further details are provided in [Table 3-5](#).

Table 3-5: Study periods vs scheduled assessments

Period	Days relative to date of first dose in EP0132	Scheduled assessment visit ^a	Scheduled assessment visit (days)
Months 1 to 3	1 to 90	MEV, Month 3	91
Months 4 to 6	91 to 180	FEV, Month 6	183
Months 7 to 9	181 to 270	MEV, Month 9	274
Months 10 to 12	271 to 360	YEV, Month 12	365
Months 13 to 15	361 to 450	MEV, Month 15	457
Months 16 to 18	451 to 540	FEV, Month 18	548

Table 3-5: Study periods vs scheduled assessments

Period	Days relative to date of first dose in EP0132	Scheduled assessment visit ^a	Scheduled assessment visit (days)
Months 19 to 21	541 to 630	MEV, Month 21	639
Months 22 to 24	631 to 720	YEV, Month 24	731
Months 25 to 27	721 to 810	MEV, Month 27	822
Months 28 to 30	811 to 900	FEV, Month 30	913
Months 31 to 33	901 to 990	MEV, Month 33	1004
Months 34 to 36	991 to 1080	YEV, Month 36	1096

^a Scheduled assessments are relative to the date of EV.

EV=Entry Visit, FEV=Full Evaluation visit, MEV=minimal evaluation visit, YEV=Yearly evaluation visit.

For efficacy analyses, data collected after Months 22 to 24 or Months 19 to 24, but prior to the Month 24 YEV, will be included only within summaries presenting the Evaluation Period or Overall Period. The Evaluation Period and Overall Period are defined in [Section 3.3.2](#). For safety analyses, data will be included from all 3-month periods both prior and post the Month 24 YEV.

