1.2 Schema

Table 1–1: EP0132 schema

| Study Period | Evaluation Period | | | | | | | | Down-Titration Period | Safety Period |
|---------------|--|------------------------------|--|--|--|--------------------------|----------------------|---------------|---------------------------------------|--|
| | EV | TC ^a | MEV | FEV | MEV | YEV | FV | EDV | | |
| Visit Type | EV | TC ^a | MEV | FEV | MEV | YEV | FV | EDV | DTV | SV |
| Visit Timing | Y1, D1 | Y1, D14 | Y1, M3/ Y2, M15 | Y1, M6/ Y2, M18 | Y1, M9/ Y2, M21 | Y1, M12 | Y2, M24 ^c | As needed | | |
| Visit Window | ±7 Days | ±2 Days | ±7 Days | ±7 Days | ±7 Days | ±7 Days | ±7 Days | | | |
| Frequency | | | 3 months after EV and 3 months after YEV for every year of participation | 6 months after EV and 6 months after YEV for every year of participation | 9 months after EV and 9 months after YEV for every year of participation | 12 months after EV | | | | 2 weeks after last dose of study drug |
| BRV Treatment | 100mg/day (2mg/kg/day for participants weighing less than 50kg) | Individual dose ^b | | | | | | | Reduce max dose by ½ until 1mg/kg/day | BRV-free period |
| Duration | ≥2 years ^c | | | | | | | Up to 4 weeks | 2 weeks | |

BRV=brivaracetam; CAE=childhood absence epilepsy; D=Day; DTV=Down-titration Visit; EDV=Early Discontinuation Visit; EV=Entry Visit; FEV=Full Evaluation Visit; FV=Final Visit; JAE=juvenile absence epilepsy; max=maximum; M=month; MEV=Minimal Evaluation Visit; SV=Safety Visit; TC=telephone call; Y=treatment year; YEV=Yearly Evaluation Visit

^a Study participants will be contacted after 2 weeks (±2 days) to check for appropriateness of dose.

^b Participants will receive 100mg/day upon entry into EP0132. The dose may be adjusted after 3 days in the range of 50 to 200mg/day (or equivalent dose of 1 to 4mg/kg/day for study participants weighing less than 50kg) based on the individual needs.

^c The duration of the study per study participant will be 2 years at minimum, until approval of BRV for the indication of CAE or JAE has been obtained for pediatric participants in their age range, until a managed access program is established as allowed per country specific requirements in addition to legal and regulatory guidelines, or until the investigational product development in the related age range of the pediatric population indication is stopped by the Sponsor, whichever comes first.

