A separate summary of the number of participants in the SS starting and completing each 3-month period within the Evaluation Period will be summarized. A listing of the 3-month periods and associated period start and end dates will also be presented. Note if a participant completes the study (attends an FV) or discontinues from the study (attends an EDV) prior to the end of the 90-day period they are considered as not completing the 3-month period.

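### The 3-month entry rule puts every on-schedule Month 24 finisher into the Months 25-27 adverse event summaries with about 4 to 18 of 90 days at risk, diluting that period's crude percentages

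*SAP*

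**What the plan says.** SAP 3.3.3 sets the analysis calendar: "A month is defined as 30 days and time intervals based on monthly durations are defined as a multiple of 30 days". Table 3-3, counted from first dose, puts Months 22 to 24 at Days 631 to 720 and Months 25 to 27 at Days 721 to 810. Visits follow another calendar: "Assessment visits are scheduled based on months calculated as 365.25/12". The SAP states the resulting gap itself: "the 19 to 24 month period would end at 720 days whereas the Month 24 visit is scheduled at 731 days". The protocol schema (Section 1.2) gives ±7 days for both the yearly and the final visit.

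The Evaluation Period runs to the Final Visit (FV) inclusive for completers (SAP 3.3.2). For adverse events, "participants will be included in 3-month period summaries if the end date of their Evaluation Period is on or after the first day" of the period. SAP 3.3.10 applies the same condition to modal dose, whatever number of days was spent in the period. The Table 3-3 footnote says of Months 25 onward: "These 3-month periods are only applicable for a subset of participants who remain in the EP0132 study past Month 24".

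For efficacy, SAP 3.3.3 keeps data falling after Day 720 but before the Month 24 visit out of the interval summaries. Safety is treated differently: "For safety analyses, data will be included from all 3-month periods both prior and post the Month 24 YEV". SAP 10.2.1 reports numbers and percentages of participants with each event, for the Overall Period, the Evaluation Period and each 3-month period. One overall summary is also given by modal dose for each 3-month period.

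**The concern.** The two calendars drift apart by 11 days at Month 24, and the entry rule looks only at whether a participant's Evaluation Period touches the first day of a period. Someone who finishes as planned at Month 24 is then counted in full in the Months 25-27 denominator, while only events with onset between Day 721 and the FV can enter the numerator.

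If many participants finish at Month 24, the Months 25-27 column is made up mostly of people seen for a week or two. Set beside Months 22-24, where the same people contributed 90 days, it would show a drop in event percentages that reflects observation time, not tolerability. The modal-dose version has the same defect, and a finisher's modal dose for the period would rest on those few days.

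The SAP does guard against short exposure elsewhere. The diary-based non-absence seizure percentages (SAP 10.5.2) require 80% of diary days, that is 72 of 90, which a finisher with at most 18 days cannot meet. The adverse event tables have no such guard, and no exposure-adjusted rate is planned: participant-years appear only in the exposure table (SAP 10.1).

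**Working it through.** **The plan's own days.** Period end = 30 × month, so 30 × 24 = Day 720. Visit day = month × 365.25/12, so 24 × 30.4375 = 730.5, rounded to Day 731. Both match SAP 3.3.3, and all twelve visit days in Table 3-5 reproduce in the same way.

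**Who enters Months 25-27.** The FV window is 731 − 7 = Day 724 to 731 + 7 = Day 738. The rule needs an Evaluation Period end on or after Day 721. Even Day 724 qualifies, so every on-schedule Month 24 finisher enters. The default denominator in SAP 3.2 (at least one assessment in the interval) would admit them too, because the FV itself falls inside Days 721 to 810.

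**Days at risk** = FV day − 720:

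- earliest: 724 − 720 = 4
- nominal: 731 − 720 = 11
- latest: 738 − 720 = 18

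Visits are counted from the Entry Visit and periods from first dose. SAP 3.3.2 expects first dose on the evening of the Entry Visit, so the two normally coincide. If first dose is a day later the range is 3 to 17; if the Entry Visit is counted as Day 0 it is 5 to 19.

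**Dilution (illustration).** The 90-day risk p and the share continuing are assumptions. With a constant hazard, the risk over d days is 1 − (1 − p)^(d/90). For p = 20% and d = 11: 1 − 0.8^(11/90) = 2.69%. At 4 days it is 1.0% and at 18 days 4.4%. If continuers stay the full 90 days:

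| Finish / continue | Calculation | Reported in Months 25-27 |
|---|---|---|
| 90% / 10% | 0.90 × 2.69 + 0.10 × 20 | 4.4% |
| 80% / 20% | 0.80 × 2.69 + 0.20 × 20 | 6.2% |
| 60% / 40% | 0.60 × 2.69 + 0.40 × 20 | 9.6% |
| 50% / 50% | 0.50 × 2.69 + 0.50 × 20 | 11.3% |
| 25% / 75% | 0.25 × 2.69 + 0.75 × 20 | 15.7% |

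Using 4 or 18 days in place of 11 moves the first row to 2.9% or 5.9%. With p = 40%, the 90/10 and 50/50 splits give 9.4% and 23.0%.

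**Later visits.** The gap grows. An FV at Month 27 (Day 822, period end Day 810) gives 5 to 19 days in Months 28-30; at Month 36 (Day 1096 against Day 1080) it gives 9 to 23 days in the next period.

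**The case against.** **The footnote.** With 30-day months, Day 731 is past Month 24, so a finisher could satisfy both the footnote and the entry rule, and a flat contradiction is not shown. That is fair. But on that reading the footnote singles out almost nobody, since everyone attending the Month 24 visit on time would belong to its subset. The SAP's version history, explaining the change to Section 8.1, describes those continuing beyond two years as a small group. The intent is clear enough, and the rule does not carry it out.

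**The primary endpoint.** A reader might infer that the primary safety result, or everything after Month 24, is distorted. The documents do not support that. The primary measure is incidence of treatment-emergent events, also reported over the Overall and Evaluation Periods, where no finisher's time is cut up. Month 24 finishers do not reach Months 28-30. Nothing is tested formally.

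**Disposition.** A reader might also fear that the count of 3-month periods started and completed (SAP 5.1.1) will look like a wave of dropout. That section says openly that a participant who attends an FV "prior to the end of the 90-day period they are considered as not completing the 3-month period", and study completion and discontinuation with reasons are tabulated separately. Those counts would expose the short exposure, though they do not correct the percentages.

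**Size and direction.** The rates and splits are assumed. The FV includes full examinations, laboratory tests and an ECG, and clinically relevant findings become adverse events. Any given an onset date at the FV would fall in Months 25-27 and partly offset the dilution. This stands: the direction is the expected one, but the size cannot be fixed from the documents.

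**Conclusion.** The point holds for the 3-month adverse event and modal-dose summaries. Under the SAP's stated rules, every on-schedule Month 24 finisher enters Months 25-27 with about 4 to 18 of 90 days, 11 at the nominal visit day. If the event hazard is roughly constant, the crude percentages for that period are too low for the participants it is meant to describe. At a true 90-day risk of 20%, the reported figure would be about 4% to 10% when 90% to 60% finish at Month 24. This rests on the assumed rate and split, and on continuers staying the full 90 days.

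The problem recurs in the period following any later visit used as the FV. It does not touch Overall or Evaluation Period incidence. It is a misleading figure in descriptive tables over time, worth correcting because the SAP has already recognised the gap and the correction is cheap.

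**What to change.** In SAP 3.3.3 and 3.3.10, for the 3-month adverse event and modal-dose summaries:

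- When the FV is an on-schedule completion visit (Month 24 or any later scheduled visit), do not count that participant in a period starting after the end of the period matched to that visit in Table 3-5. A Month 24 FV is matched to Months 22 to 24.
- Report such a participant's events from the end of that period to the FV in the Evaluation and Overall Period tables only, as the SAP already does for efficacy.
- Keep early discontinuers and continuers in the period they entered, so that events leading to discontinuation are not moved.
- Reword the Table 3-3 footnote to match, and footnote the disposition table.

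Alternatively, keep the entry rule and show person-time or exposure-adjusted incidence for each 3-month period.

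Two simpler repairs fall short. Admitting only participants followed beyond Day 738 and moving the others' events into Months 22-24 makes entry depend on later follow-up. It also shifts events of those who discontinue early on Days 721 to 738, and stretches the earlier period to as much as 738 − 631 + 1 = 108 days for some participants only. Redefining months as 365.25/12 days would start Months 25-27 at Day 732, so finishers 1 to 7 days after the nominal visit day would still enter with 1 to 7 days.

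The cost is a few sentences and one derivation change. A few days of finishers' adverse event data would appear only in the Evaluation and Overall Period tables.
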